Safety planning is an evidence-based brief intervention in which patients and study provider working together to identify triggers of suicidal ideation (e.g., a fight with spouse). The patients and study provider then identify a set of coping strategies that can be used to manage the difficult feelings that may emerge. These strategies include internal strategies (e.g., deep breathing), distracting activities (e.g., go bowling), and help-seeking behaviors (e.g., call a friend or a mental health professional). The patient and study provider also identify emergency contacts for the patient (e.g., crisis line) and ways to reduce access to means of self-harm.

The second (2nd) through fourth (4th) sessions of Problem-solving Treatment focus on problem-orientation. Problem-orientation refers to the way an individual is predisposed to think and feel about their problems. It is comprised of the attitudes, beliefs and expectations a person has about the likelihood of their successful problem-solving. A positive problem orientation leads to increased confidence and recognition that with adequate investment of time and effort, most problems can be addressed. To improve problem orientation, the Patient is taught to identify their "red flags" or threats to a positive problem orientation (e.g., feeling overwhelmed). They then identify strategies that will create a more positive problem orientation (e.g., relaxation exercise, positive self-talk).

In sessions five (5) through eight (8), Patients are taught a 5-step planful problem-solving approach we call S-O-L-V-E. Steps of S-O-L-V-E include:

1. **State** the problem and goals
2. **Option** identification
3. **List** pros and cons of options
4. **Visualize** the steps
5. **Evaluate** success

In sessions nine (9) through eleven (11), patients practice the entire problem-solving approach for a different problem each week with a real-life example from their actual experience.

Finally, session 12 focuses on maintenance of success and preventing backsliding. In PST, the patient solves problems that are occurring in their daily life. At the Study Provider's or PI's discretion, the treatment or protocol may vary in order to meet a Veteran's needs (e.g., changing the order of the information given, having an additional session if feasible).

Attentional control:

Our control will be remote attentional control which will focus on discussing weekly stressors in a supportive, non-directive way.²⁴

Session content of attentional control is patient-driven, and sessions focus on emphasizing the patients' strengths, following patients' emotional affect, and building a therapeutic alliance. Participants will be asked to generate the topic they would like to discuss for the session and will be provided a new worksheet to complete between sessions noting emotional events throughout their week ("A time when I felt stressed was ...") This will help identify experiences for discussion in session. These worksheets will be provided to participants.

As Veteran safety is our primary concern, if a pre-existing VA safety plan is not found in the Veteran's medical record, a safety plan will be developed collaboratively between Veteran and provider during the first session. Safety planning is an evidence-based brief intervention that identifies triggers of suicidal ideation as well as spells out a concrete set of coping strategies that can be used to manage the difficult feelings that may threaten an impending crisis. Throughout the treatment, the provider will use clinical judgment to monitor the Veterans suicidal ideation. Participants and their usual care providers will be informed that: sessions are designed to be supportive and non-directive; providers will not engage in problem-solving; and that attentional control is not a treatment for suicidal ideation. If a patient is not receiving treatment for their suicidal ideation, we will recommend treatment for suicidal ideation to the patient and their usual care provider.

Treatment Fidelity: We have planned a multi-step approach to ensuring fidelity, competence and treatment differentiation for both treatments (Table 1). We audio record each session and code ~20% for fidelity. For the attentional control we will assess for the active ingredients of this treatment (e.g., empathy) as well as identifying if there is any inappropriate drift into PST. This will enable us to ensure that active ingredients of the two treatments remain separate. Providers are highly supervised, and we intervene if there is poor adherence to treatment or low competency. We used NIH's Behavioral Change Consortium's treatment fidelity framework and Perpletchikova recommendations^{65,66} on treatment integrity to guide the development of fidelity monitoring.

Table 1 – Treatment Integrity Approach

Treatment integrity procedure	Provider treatment fidelity	Provider competence	Treatment differentiation
Assessment of treatment integrity	Direct observation in peer supervision; therapy checklist after each session; record length of time for each session.	Direct observation in individual and peer supervision.	Direct observation in individual and peer supervision.
Accuracy of data	A random sample (20%) of collected tapes is examined, sampled across study providers, treatment phases, situations, cases and sessions.		Code the control for use of PST.
Rating integrity	Raters are highly trained; interrater reliability is assessed; multiple raters are used.		
Operational definition	Specific treatment manual with information about the theory & sequencing of techniques.		
Training of providers	Three days of didactic instruction for each treatment; listen to treatments delivered by other providers; role-play with other providers; on-going bi-weekly feedback and peer training.		
Supervision of study providers	Study providers attend twice-weekly peer & weekly individual supervision; supervision includes observation; review of adherence checklists; if a study provider fails to meet criteria s/he will receive more intensive supervision.		

Assessments: Assessments will consist of the Veterans completing questionnaires and a short battery of neuropsychological tests. Additionally, the specified support person of the Veteran will be asked to complete questionnaires. Veterans (and their support person) can complete the questionnaire packets

through Qualtrics, the U.S. mail (the packet would be mailed to the Veteran along with a pre-paid envelope to return the packet), and/or over the telephone with a member of the study team. The neuropsychological battery will be completed through Millisecond's Inquisit Web, a software package designed to administer neuropsychological measures online, as well as over the phone to administer the means-end problem-solving task. We will make a concerted effort to remind Veterans with letters and phone calls to complete and return questionnaires, and also to complete the neuropsychological battery. If needed, we will resend questionnaire packets to Veterans and/or their support person. We will also collect data from the Veterans' medical record about their diagnoses, treatments, medications.

Assessments will be completed at four time points:

- **Baseline:** questionnaire packet, neuropsychological battery, and support person questionnaire packet will be collected at the start of the study (~2 hours for questionnaire packet and neuropsychological battery; ~5 minutes for the support person questionnaire packet)
- **4-week, mid treatment:** questionnaire packet will be collected after completion of the 4th session of either Problem-solving Treatment or attentional control (~30 minutes)
- **Post-treatment:** questionnaire packet, neuropsychological battery, and support person questionnaire packet will be collected after the 12th session of either Problem-solving Treatment or attentional control (~2 hours for questionnaire packet and neuropsychological battery; ~5 minutes for the support person questionnaire packet)
- **6-month follow-up assessment:** questionnaire packet will be collected ~6 months after the 12th session of either Problem-solving Treatment or attentional control (~1 hour)

See below for Table 2, which outlines when the measures and neuropsychological tests will be administered, along with a summary of each.

Table 2 – Measures administered at each timepoint

Domain	Study Instruments	Screening	Baseline	4 week	Post Treatment	6 Months
Aim 1: Primary Outcome	Social Problem-Solving Inventory Revised [SPSI-R] *		X	X	X	X
	Neuropsych Assessment: Emotional Go No-Go		X		X	
	Neuropsych Assessment: Means-End Problem-Solving Task [MEPS]		X		X	
	Neuropsych Assessment: Iowa Gambling Task		X		X	
	Neuropsych Assessment: Stroop Test		X		X	
Aim 1: Secondary Outcome	Interpersonal Needs Questionnaire [INQ]		X	X	X	X
Aim 2: Exploratory Outcome	Columbia-Suicide Severity Rating Scale [C-SSRS]	X	X		X	X
	Suicide Ideation Questionnaire [SIQ]		X	X	X	X
	Suicide-Related Coping Scale		X	X	X	X
	Pain Disability Index [PDI]		X	X	X	X
	Brief Pain Inventory [BPI]	X	X	X	X	X
Participation Characterization and Screening Instruments	Healthcare Access [HCA]		X		X	
	Demographic * / Treatment Survey	X	X		X	
	Post-Traumatic Stress Disorder Checklist [PCL]		X		X	
	The Patient Health Questionnaire-9 [PHQ-9]		X		X	X
	Patient Health Questionnaire [PHQ-15]		X		X	X
	World Health Organization Disability Assessment Schedule [WHO-DAS 2.0]		X		X	
	MOS Social Support		X		X	
	Audit-C		X		X	
	Cognitive Failures Questionnaire		X		X	X
	Coronavirus Stressor Survey	X				
Quality of Treatment Delivery	Working Alliance Inventory [WAI]			X	X	
	Patient Global Impression of Change [PGIC]				X	
	Client Satisfaction Survey				X	

* = Veteran's support person will complete their own version

*For Veterans' who we were unable to capture the Coronavirus Stressor Survey at baseline (due to timing of its addition to the protocol), we will attempt to capture it at a follow-up timepoint (e.g. 4 week, post treatment, or 6-month follow-up assessment).

Involvement in Alternate Treatments: Throughout the course of their participation, Veterans will be allowed to begin a new treatment, continue with current medical regimen/treatments, or make changes to their existing medical regimen. For patients not currently in mental health treatment, we will communicate the availability and appropriateness of mental health services to the patient and their established provider. Adherence to medical protocols and participation in alternate treatments will be evaluated by a questionnaire during assessments and this will be controlled for in analyses.

Communication with Other Providers: In both arms, the Veteran can continue to receive care from their established providers. This includes their primary care provider and mental health provider (if they have one). If deemed clinically appropriate by a study provider, we will reach out to the Veteran's local

providers at screening to communicate the patient's active suicidal ideation. When the Veteran consents to participate in the study, the study team will send the primary care and mental health providers a letter describing the study, letting the provider know about the patient's suicidal ideation, and inviting them to contact the study team with any questions or concerns. **The letter will additionally detail that their Veteran's participation in the research study is not a replacement for standard clinical care.** During baseline, a study provider will assess suicide risk using the C-SSRS.²⁶ If the baseline C-SSRS score represents an increase from that at screening, the study provider will communicate this to the Veteran's established providers. If providers have any concern about Veteran safety at any point during their participation, a provider will reach out to the Veteran's local health care team. Additionally, providers will place a note in the electronic medical record after every session with the Veteran.

We will contact participants' health care providers at any time during the study if we have a concern about the Veteran's health and/or safety. For urgent matters, the study providers will call the established providers and/or send encrypted emails.

Clinical Training and Supervision: Study providers will be licensed and credentialed mental health providers (e.g., psychologist) or mental health trainees (e.g., fellows) supervised by a licensed and credentialed mental health provider. Before seeing patients, all study providers will first receive extensive training on problem-solving and attentional control. They will listen to all 12 sessions of our tailored PST and observe [name] problem-solving video. They then will role play the PST and attentional control. Only when it is determined that they are ready, can they communicate with their first patient. Study providers attend twice-weekly peer supervision. The WRIISC has a training program and allows psychology trainees to become study providers. Trainees will receive individual supervision. During these sessions, the team reviews audio tapes, and discusses problems and successes.

Study providers will each see equal numbers of problem-solving treatment and attentional control patients to ensure that the level of providers is balanced between the arms.

Additionally, [name] will lead a monthly meeting to discuss study progress, successes, difficulties and data analysis. [name] will meet with study personnel once a week to set goals and discuss priorities. [name] will meet weekly with the study coordinator ([name]) and head of her mental health team ([name]). [name] will meet daily with the research assistant to guide recruitment and study progress. [name] will provide weekly supervision for all study providers and, as needed, for administering the C-SSRS.

Minimizing Attrition: We will schedule appointments at a time most convenient for the Veteran (including evenings). We will attempt to make reminder phone calls approximately 24 hours prior to their session. It is our experience that missing sessions, no matter what the reason, often leads to attrition. Therefore, the study staff will try to call a Veteran within 24 hours if they miss a session.

Primary Outcomes:

Social Problem-Solving Inventory-Revised (SPSI-R)⁷⁰. The SPSI-R measures problem-solving that is sensitive to change. In clinical research, the SPSI-R has been successfully used to elicit meaningful self-appraisals. The questionnaire is 52 items long. We will use the total score, as well as the 5 subscales. The

SPSI-R is internally consistent (alpha=.90) and reliable (r=.87) and has been used as an outcome of PST. Support person will also complete a version of this.

Affective Go/No Go⁷¹. This is a neuropsychological test that measures attention and impulse control. Inhibiting impulses is a key component of preventing impulsive behavior that can lead to suicide. Indeed, scores on the Go/No Go have been shown to predict suicidal behavior.

Means-End Problem-Solving Task⁷³. The MEPS is a neuropsychological test that consists of a series of scenarios, with each one identifying the beginning and end of a story. The subject's task is to come up with the middle of the story. Stories are scored according to how many steps the patient identifies in reaching the end. This instrument captures a crucial element of problem-solving: identifying the steps (i.e., means) that will lead to goal attainment (i.e., end). This aspect of problem-solving is directly relevant to patients with pain whose limited set of identified means includes suicide. An increase in effective means generated is expected to drive reduction in suicide ideation. The MEPS has been used in suicide research and has shown that suicide attempters generate fewer relevant means than both non-suicidal psychiatric controls and non-psychiatric controls.⁷⁴

Iowa Gambling Task⁷⁵. The Iowa gambling task is a neuropsychological task of problem-solving. The goal of the task is to make "money". Participants are presented with four decks of cards and have to choose cards from these decks to make "money". Subjects have the opportunity to learn about the gains and losses associated with each deck in order to maximize profit. Performance on this task has been shown to change after problem-solving therapy.⁷⁶

Emotional Stroop^{77,78}. The emotional Stroop is a test of response inhibition. This is a critical skill needed to refrain from engaging in suicidal behavior.⁷⁹ Our preliminary data suggest that Stroop is responsive to change in clinical trials for suicidal behavior.

Caregiver Social Problem-Solving Inventory-Revised (SPSI)⁷⁰. A support person of the Veteran will be identified by the patient and invited to complete the SPSI to provide their perspective of the patient's problem-solving ability.

Secondary Outcome:

Interpersonal Needs Questionnaire (INQ).⁸⁰ Feelings of burdensomeness and belongingness will be measured by the Interpersonal Needs Questionnaire (INQ). The INQ is an 18-item self-report questionnaire. Scale items have high levels of internal consistency, and findings from prior investigations have also supported the construct, convergent, and predictive validity of this measure.

Exploratory Outcome:

Columbia-Suicide Severity Rating Scale (C-SSRS).²⁶ The C-SSRS is the gold standard for suicide assessment and measures level and intensity of suicidal ideation, planning and preparation for suicidal behavior, and method and lethality of recent and past lifetime suicidal behavior. During assessment, this measure will be administered by study personnel. To determine eligibility, we will use the level of suicidal ideation. Patients will be eligible who have a score of 2 (have you actually had any thoughts of killing yourself?), 3 (have you been thinking about how you might do this?) or 4 (Have you had these thoughts and had some intention of acting on them?). The intensity of ideation subscale (the summed score from five

separate items on Part II of the C-SSRS; subscale range = 2-25) will be the primary dependent variable for the fully powered clinical trial. The intensity of ideation asks about the intensity of ideation in the past 6 months (e.g., the frequency, duration controllability).

Suicide Ideation Questionnaire (SIQ).⁸¹ The SIQ is a 30-item self-report instrument designed to assess thoughts about suicide experienced during the prior month. SIQ has strong internal consistency ($\alpha = .97$) and construct validity. This measure will allow for supplementary investigation of ideation.

Suicide-Related Coping Scale.²⁷ The Suicide-Related Coping Scale captures an individual's perceived ability to use internal and external coping to problem-solve suicidal thoughts and urges. This measure was validated in a Veteran sample. The items in this measure capture the types of skills we expect Veterans to be able to use after learning problem-solving (i.e., "I recognize the circumstances that make me suicidal")

Pain Disability Index (PDI).³¹ Is a 7-item measure of the impact of pain on daily activities and social relationships. It will be used to assess disability from pain.

Brief Pain Inventory (BPI).²⁸ Pain will be assessed using the BPI. The BPI is a 10-item measure of pain severity and interference. The total score is sensitive to change with 1 point considered clinically meaningful.

Self-Report Participant Characterization and Screening Instruments:

Demographic/Treatment Survey. This is a brief questionnaire designed to elicit basic demographic information including: medical conditions; treatment; sex; age; marital status; etc. Support person will also complete a version of the demographic questionnaire.

Post-Traumatic Stress Disorder Checklist (PCL).⁸² The twenty item National Center for PTSD Checklist (PCL) has been updated to align with the newest PTSD criteria and will be used to assess PTSD. The PCL is a valid and reliable measure of PTSD symptoms.

The Patient Health Questionnaire-9 (PHQ-9).⁸³ The PHQ-9 is a 9-item self-report questionnaire that assesses the frequency of depressive symptoms over the past two weeks. The total score of the PHQ-9 has also been used as indicative of depression severity and is sensitive to clinical change.

Patient Health Questionnaire (PHQ-15).⁸⁴ The PHQ-15 measures physical symptoms. The PHQ-15 was validated on a sample of 6,000 and found to be reliable, valid and responsive to change

World Health Organization Disability Assessment Schedule (WHO-DAS 2.0).⁶² The WHO-DAS measures impairment in completing daily activities and social relationships due to physical and mental health conditions. The items of the WHODAS have a factor loading on composite score of 0.82 to 0.98.

MOS Social Support.⁸⁵ The MOS Social Support measure captures perception of access to available supports. The MOS Social Support has high convergent and divergent validity in addition to excellent reliability.

Audit-C.⁸⁶ The audit-c captures alcohol abuse and is predictive of alcohol abuse problems.

Coronavirus Stressor Survey. This captures experience with COVID-19 and difficulties that have been encountered due to it.

Self-Report Measures of the Quality of Treatment Delivery:

Working Alliance Inventory (WAI) – Self.⁸⁷ The working alliance assesses the participants' perception of their relationship with their study provider. The working alliance has excellent reliability (.80) and validity.

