Study Population Participants will consist of 60 Veterans with chronic pain and active suicide ideation. Participants will be randomized to either remote Problem-solving Treatment or remote attentional control (n=30/group). Consistent with recommendations for preliminary analyses, sample size was determined based on estimates of feasibility during the study timeframe.^{90,91}

Subject Identification and Recruitment: Any Veteran who resides within the United States may be invited to participate in the study. During the phone screening, we will request verbal consent and inclusion/exclusion criteria will be evaluated. Veterans may be recruited from anywhere in the nation. Potential participants may be identified through the following: VINCI, VISTA and/or CPRS, REACH VET, the Managerial Accounting Office (MCAO), the VA Epidemiology Program, the VA Office of Public Health Gulf War Registry, the Defense Manpower Data Center (DMDC) of the Department of Defense (DoD), VADIR (Veteran Administrative DoD Identity Repository), WRIISC Clinical and Operations Databases. We may also reach out to Veterans who have both participated in recent studies and expressed interest in being contacted. We will request from VINCI, the DMDC, VADIR, the VA Epidemiology Program, and VA Office of Public Health Gulf War Registry to provide a list of Veterans who possibly meet our inclusion criteria and reside nationally. Data elements requested can include the following: name, date of birth, social security numbers, address, contact phone number(s), vital statistics, period of combat (combat pay records) and/or service medals, status of deployment.

We will also use the following methods to identify and recruit potential participants: referrals, standard mail, telephone, flyers, and advertisements. This includes: 1. planned conferences, satellite broadcasts, and other educational workshops or meetings for providers or Veterans; 2. VA facilities and affiliated ambulatory services including community-based outpatient clinics (CBOCs); 3. community locations (e.g., Home Depot); 4. Veteran-related events such as job fairs; 5. newspapers/newsletters; 6. websites relevant to Veterans (e.g., American Legions); 7. VA and Veteran-related social media; and 8. websites relevant to recruitment (e.g. clinicaltrials.gov).

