For the support people that are interested in participating, we will mail them a confirmation letter detailing their appointment date/time, a study information sheet, the baseline assessment packet, and a copy of the written informed consent and HIPAA so they can review the study procedures and formulate questions prior to their subsequent telephone appointment. We are obtaining a waiver of documentation of consent for the Veteran's support person and will ask their support person, at the end

of reviewing the informed consent and answering any questions, if she/he agrees to participate. This will take approximately 10 minutes to complete and will primarily be conducted over the phone.

Inclusion Criteria: (a) has a VA primary care provider and has had an in-person visit with a VA provider in the past year; (b) pain that is: (b1) musculoskeletal, defined as regional (joints, limbs, back, neck) or more generalized (chronic widespread pain); (b2) moderately severe, defined as a Brief Pain Inventory (BPI) intensity item score of 5 or higher for either “average” or “worst” pain in the past week; and (b3) persistent, (i.e., ≥ 3 months); (c) active suicidal ideation defined as scoring a 2 to 4 on the C-SSRS.

Exclusion Criteria: (a) life-threatening condition; (b) severe cognitive impairment; (c) psychotic disorder; (d) pregnant or plans to become pregnant in the next year; (e) suicide attempt in the past year or hospitalization for suicide risk in the past year.

Randomization Procedures: Since randomization may fail to ensure equivalent levels of our primary dependent variable, we will enroll Veterans in matched pairs and use an urn randomization procedure designed to maximize the equivalence of groups based on selected matching criteria ⁵⁹ or “urns.” Matching will be based on screening suicidal ideation intensity and problem-solving ability with members of a pair falling within +/- 20% of one another to ensure that the distribution is comparable between groups. This matching rule permits wide latitude in scores, but if a Veteran is not matched s/he will be offered Problem-solving Treatment outside of the study. We will use the computer program developed for Project MATCH to generate the randomization schedule. The study coordinator will conduct the randomization. Research investigators (including the Principal Investigator) will be blind to study assignment.

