When a participant is withdrawn from the research for safety concerns, our team will retain clinical responsibility until continuing care is successfully transferred to the appropriate provider (e.g., emergency department, hospitalization, psychiatrist, local suicide prevention coordinator, primary care provider). The following situations will necessitate participant withdrawal from the research (but not clinical care):

- Suicide attempt
- Indication that participant has developed definite intent to carry out a suicide plan, as measured by endorsement of item 5 on Section I of the C-SSRS.
- In addition, if there is a significant increase in the severity of suicidal ideation the participant will be reviewed by an internal study safety team comprised of 3 study investigators to determine appropriateness for continued participation. Increased risk will include an increase of 2 points on the C-SSRS from a participant's baseline level (e.g., moving from a baseline C-SSRS score of 2 [i.e., thoughts of killing oneself without any associated method or intent] to a C-SSRS score of 4 [i.e., suicidal thoughts with some, limited intent to act on them]).

Data Analysis Plan: We will explore the data using scatterplot graphs and calculating the means, standard deviations, proportions, histograms, etc. to explore the distributions of the data, identify outliers and calculate correlations between variables. We will calculate the percent change from baseline for each measure. We will also calculate the effect size (Cohen's D) for the change in each arm from pre to post treatment and calculate the effect size of the change in treatment between arms. Consistent with best practices for preliminary data analysis, we will not calculate statistical significance as we are not be powered to find an effect.^{90,91} The analyses will be conducted with intent to treat approach.

Best practices for determining improvement in executive functioning include using self-report, objective and support person report. While it is not expected all measures will show improvement due to variability in the assessment approaches, there should be an indication of clinically significant improvement across multiple assessments. Our preliminary data is consistent with previous research that finds PST has a moderate effect on self-report of problem-solving deficits (Cohen's D >0.22)^{45,46} as

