compared to control and a small effect on objective measures of problem-solving deficits (Cohen's $D > 0.15$) as compared to control - and these are clinically significant.

We will conclude that our trial shows support for target engagement if we find a clinically significant effect size for PST as compared to control for two of the three domains (self-report Cohen's $D > .22$; objective neuropsychological tests Cohen's $D > .15$ for at least two measures; support person report Cohen's $D > .22$) and no domain showing support for control over PST (self-report Cohen's $D > .22$ in support of control; objective neuropsychological tests Cohen's $D > .15$ for at least two measures in support of control; support person report Cohen's $D > .22$ in support of control). We will also explore if there are differences in effects based on level of provider training.

If data from this study suggest converting the trial into a fully-powered clinical trial, we will consider the analyses of getting the effect size as an interim analysis to inform the planning of R01, and adjust the sample size in the R01 using the method of, for instance, sample size re-estimation approach, to appropriately adjust for the alpha level for the test at the final data analysis of the full trial.

Some of the data analysis will be completed by our collaborator at Rutgers University School of Public Health. If data needs to be physically sent to our collaborator at Rutgers University School of Public Health, a DUA will be executed prior to sending.

Benefits: There are no direct benefits to subjects. This study will enable us to learn more about treatments that may help individuals with pain and active suicide ideation. Some participants may experience improvement in pain, disability, and suicide ideation.

Protected Health Information:

Privacy and Confidentiality of Data

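### Allocation is balanced on two screening scores that the between-arm effect size does not use, which costs some precision once matched pairs break (minor)

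*Combined protocol and SAP*

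**What the plan says.** Under Randomization Procedures the protocol states "we will enroll Veterans in matched pairs and use an urn randomization procedure designed to maximize the equivalence of groups". It adds: "Matching will be based on screening suicidal ideation intensity and problem-solving ability with members of a pair falling within +/- 20% of one another". A Veteran who cannot be matched is offered the treatment outside the study. The section does not say whether the two members of a pair must go to opposite arms.

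The Data Analysis Plan sets out descriptive statistics, percent change and a within-arm Cohen's d. For the comparison of arms, it says the team will "calculate the effect size of the change in treatment between arms". It names no pair term, no urn factor and no matching score. It specifies intent to treat and gives no missing-data method. It plans no test ("we will not calculate statistical significance as we are not be powered to find an effect") and mentions no confidence interval. Target engagement is judged by comparing point estimates with fixed cut-offs: "self-report Cohen's $D > .22$; objective neuropsychological tests Cohen's $D > .15$ for at least two measures", and .22 again for the support person's report.

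The only adjustment named anywhere is under Involvement in Alternate Treatments, for adherence and other treatments. Table 2 schedules the C-SSRS at screening but no problem-solving measure there, so one of the two matching scores is not identified.

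**The concern.** A plan that constrains allocation on two scores treats them as prognostic. An analysis that then leaves them out discards information the trial has already collected.

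With every pair complete and split between arms, the balance is built into the arm means and nothing is lost in the estimate. This protocol gives several reasons to expect incomplete pairs. The Safety Plan requires withdrawal from the research after certain events. Minimizing Attrition says that missed sessions often lead to dropout. Veterans may also decline to name a support person, which leaves gaps in that domain even without dropout. Each broken pair gives back some of the balance.

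The Data Analysis Plan says these effect sizes will inform R01 planning and sample-size re-estimation, so their precision matters, and so will any interval placed around them.

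**Working it through.** **The plan's own figure.** The sample size is 2 × 30 = 60, and "sample size was determined based on estimates of feasibility during the study timeframe". No power, SD or dropout rate is given, so there is nothing further to reproduce.

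**Complete pairs, opposite arms.** The mean of 30 within-pair differences equals the difference of the two arm means, so the point estimate is the same either way. Only the standard error differs. Near d = 0:

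- Ignoring pairs: SE = √(2/30) = 0.258. The 95% half-width is 2.002 × 0.258 = 0.517 (58 df).
- Using pairs: SE = √((2/30)(1 − r)), where r is the within-pair correlation of the outcome (assumed). The multiplier is 2.045 (29 df).

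| r (assumed) | Half-width using pairs | Excess width if pairs are ignored |
|---|---|---|
| .1 | 0.501 | 3% |
| .2 | 0.472 | 9% |
| .3 | 0.442 | 17% |
| .5 | 0.373 | 38% |

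Break-even is r = 1 − (2.002/2.045)² ≈ .04. Below that, ignoring the pairs costs nothing in width. Simulated matching within 20% on two scores induced r of about .05–.20 for change scores, so the lower rows of the table are not expected here.

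**Broken pairs.** With 20% independent dropout, 30 × 0.8² ≈ 19 pairs stay intact. With 30%, 30 × 0.7² ≈ 15 do.

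*Simulation by variance explained.* Assumed: intensity mean 13, SD 4.5, range 2–25; problem-solving coefficient of variation 30%; correlation of the two scores 0.3; pair members in opposite arms; 20% dropout; 3,000 trials per setting. The last column is without dropout.

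| Variance of change explained by the two scores (assumed) | Variance cut from adjusting | Unadjusted SE too large by | Same, no dropout |
|---|---|---|---|
| 10% | 1% | 1% | 0% |
| 25% | 6% | 10% | 12% |
| 40% | 13% | 15% | 20% |

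A separate run of 2,000 trials per setting gave variance cuts of 1%, 5% and 12%, and SE excess of 3%, 10% and 19%, all with 20% dropout.

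*Simulation from correlations.* Assumed: coefficient of variation .20–.35, screening-to-baseline correlation .8–.9, baseline-to-post correlation .3–.7; 1,500 trials per setting. Adjusting lowered the true SE by about 0–6% with 20% dropout, and by up to 8% with 30% (post scores, 0.283 to 0.261). The largest gains at 20% dropout include 0.255 to 0.240 for change scores. In variance terms that is 1 − (0.240/0.255)² ≈ 11%, in line with the table. The unadjusted SE for change scores was 0–12% too large.

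*Urn that does not force opposite arms.* In a median-split urn with 60 Veterans and 20% dropout, the unadjusted SE was only about 1%, 3% and 6% too large at 10%, 25% and 40% variance explained. Adjusting then cut the variance by about 2%, 15% and 28%. In that case the benefit is ordinary covariate adjustment, and interval width is hardly an issue.

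**Dropping incomplete pairs.** With 20% dropout, analysing complete pairs only gave an SE of about 0.27–0.31 in the same settings where the adjusted model gave about 0.24–0.28.

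**The case against.** The strongest reply is that the plan computes no standard error, interval or test, and its decision rule uses point estimates. A reader might infer that the trial's intervals will be too wide. The documents do not support that: there is no planned interval, and the excess would be near nil for an outcome that the scores predict weakly. This part of the reply stands, so the width problem is conditional on an interval being added.

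A reader might also infer that the effect size is biased or that the go/no-go rule is compromised. Neither follows. Take 24 per arm after 20% dropout and a true d of 0. Then SE = √(2/24) = 0.289, and the chance that one self-report d exceeds .22 is 22.3%. Variance cuts of 1%, 6% and 13% move it to 22.2%, 21.6% and 20.7%. In the worst case, with true d exactly .22, simulated adjusted and unadjusted estimates fell on opposite sides of .22 in about 6%, 9% and 12% of trials. The choice of model can therefore matter for a single domain, but only close to the cut-off.

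The size of the gain is also uncertain. Nothing in the documents shows that screening scores explain 25–40% of the variance of change in the Go/No-Go, gambling, Stroop, INQ or pain outcomes. For SPSI-R, part of the gain overlaps with adjusting for its own baseline.

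What remains after these points is the mismatch itself: two scores govern allocation and neither enters the effect estimate. The planned adjustment for adherence and alternate treatments does not supply them.

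**Conclusion.** The concern holds as a modest loss of precision. With complete opposite-arm pairs the point estimate is unaffected. With 20% dropout and opposite-arm pairs, leaving out the two scores costs about 0–13% of variance. If the urn does not force opposite arms, one simulation puts the cost at 2–28%, with the top figure requiring scores that explain 40% of the variance of change. An interval that ignored the matching would be about 0–20% too wide under the assumed range, which errs on the conservative side.

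All of these figures rest on assumed variance explained, score distributions and dropout, and should not be quoted as properties of this trial. They are small beside a half-width of about 0.5 set against cut-offs of .15 and .22. Minor priority, worth doing because it is nearly free.

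**What to change.** In the Data Analysis Plan, state that each between-arm effect is estimated from a linear model with arm and the two screening scores used for matching, that every randomised Veteran with outcome data is included whether or not the partner has data, and that the interval from this model is reported.

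Name the problem-solving measure used at screening and add it to Table 2. State whether pair members are always assigned to opposite arms. A sensitivity analysis with pair as a random effect is optional.

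Keep the standardiser for Cohen's d the same as the one behind the .22 and .15 cut-offs, so that adjustment does not change the scale of the decision rule.

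The cost is two degrees of freedom and a few sentences. No new data are needed, since both scores must exist for the matching to be carried out.
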